- DESIGN This is a Phase IIa, double-blind, placebo-controlled, randomized trial designed to compare the safety, tolerability, and antiviral activity of EIDD-2801 (also known as MK-4482) versus placebo as measured by viral RNA detection in symptomatic adult outpatients with coronavirus disease-2019 (COVID-19).
- DURATION 28 days. Treatment will be for 5 days with 23 days of post-treatment followup.
- SAMPLE SIZE This study will enroll up to approximately 172 fully evaluable participants in multiple study parts. If participants in a dose group drop out or otherwise have missing or unevaluable primary or key secondary virology endpoint data, additional participants may be enrolled to ensure adequate data at each dose level. The total number of participants to be enrolled will not exceed 204.

Part 1:

- Arm A (EIDD-2801 200 mg): up to approximately 22 participants
- Arm B (placebo): up to approximately 22 participants

Parts 2-4 (Optional):

- Arms C (Part 2), E (Part 3), G (Part 4) (EIDD-2801 up to 800 mg): up to approximately 12 participants per part
- Arms D (Part 2), F (Part 3), H (Part 4) (placebo): up to approximately 4 participants per part

Parts 5-9 (Optional):

- Arms I, K, M, O, Q (EIDD-2801 up to 800 mg): up to approximately 12 participants per part
- Arms J, L, N, P, R (placebo): up to approximately 4 participants per part

The dose of EIDD-2801 evaluated in Part 1 will be 200 mg BID. Doses selected for subsequent study parts may be the same, higher or lower than doses studied in previous Part(s), and will not exceed 800 mg BID. Doses

will be chosen based on emerging virology and safety data from this study and other ongoing clinical studies. Selected doses will be communicated in an official memo/protocol clarification letter. The maximum number of participants enrolled will be 204. Participants who are randomized but do not start study treatment will be replaced. All study part sizes are approximate. Study parts may be combined for randomization purposes if the same dose is planned for more than one part. Study parts enrolling at the same dose level may be enrolled simultaneously.

Study Part	Treatment Arm	Placebo Arm	Total Subjects	Projected Dose
	(n)	(n)		Level
1	A (22)	B (22)	44	200 mg
2	C (12)	D (4)	16	400 mg
3	E (12)	F (4)	16	400 mg
4	G (12)	H (4)	16	400 mg
5	I (12)	J (4)	16	TBD or 800 mg
6	K (12)	L(4)	16	TBD or 800 mg
7	M (12)	N (4)	16	TBD or 800 mg
8	O (12)	P (4)	16	TBD or 200 mg
9	Q (12)	R (4)	16	TBD or 400 mg
Total:	118	54	172	

Sample Treatment Assignment Table (Fully Evaluable Participants) (doses and order of progression subject to change)

POPULATION

Symptomatic, outpatient (at baseline), adults (aged \geq 18 years) with severe acute respiratory syndrome-coronavirus-2 (SARS-CoV-2) infection within 7 days of symptom onset.

REGIMEN In Part 1 of the study, participants will be randomized 1:1 into Arms A and B to receive active/placebo study treatment as follows: EIDD-2801 200 mg or placebo orally BID for 5 days. Enrollment for Arms A and B may be considered full when at least 24 and up to approximately 44 participants are enrolled. Enrollment in Part 1 may be interrupted to initiate enrollment in a different study Part, and may resume at a later time point. In subsequent optional study parts, participants will be randomized 3:1 to receive treatment as follows: EIDD-2801 up to 800 mg or placebo orally BID for 5 days.

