3. STUDY DESIGN

This is a Phase IIa, double-blind, placebo-controlled, randomized trial, designed to compare the safety, tolerability, and antiviral activity of EIDD-2801 versus placebo as measured by viral RNA detection in symptomatic adult outpatients with COVID-19. The study is a multicenter trial.

This study will enroll up to approximately 172 fully evaluable participants in multiple study parts. If participants in a dose group drop out or otherwise have missing or unevaluable primary or key secondary virology endpoint data, additional participants may be enrolled to ensure adequate data at each dose level. The total number of participants to be enrolled will not exceed 204.

In Part 1 of this study, up to approximately 44 participants will be randomized 1:1 to receive EIDD-2801 200 mg BID (Arm A) or placebo (Arm B) orally BID for 5 days. Enrollment in Part 1 may be interrupted to initiate enrollment in a different cohort, and may resume at a later time point. The study may continue to enroll the following optional study parts:

- In Parts 2--4, up to approximately16 participants per part will be randomized 3:1 into Arms C and D (Part 2), Arms E and F (Part 3) and Arms G and H (Part 4) to receive treatment as follows: EIDD-2801 up to 800 mg or placebo orally BID for 5 days.
- In Parts 5--9, up to approximately 16 participants per part will be randomized 3:1 into Arms I and J (Part 5), Arms K and L (Part 6), Arms M and N (Part 7), Arms O and P (Part 8), and Arms Q and R (Part 9) to receive treatment as follows: EIDD-2801 up to 800 mg or placebo orally BID for 5 days.

The dose of EIDD-2801 evaluated in Part 1 will be 200 mg BID. The doses selected for subsequent study parts may be the same, higher or lower than the dose(s) studied in previous study parts, and will not exceed 800 mg BID. Doses will be chosen based on emerging virology and safety data from this and other ongoing studies. Selected doses will be communicated in an official memo/protocol clarification letter. The maximum number of participants enrolled will be 204.

All study part sizes are approximate. Study parts may be combined for randomization purposes if the same dose is planned for more than one part. Study parts enrolling at the same dose level may be enrolled simultaneously.

(doses and order of progression subject to change)				
Study Part	Treatment Arm	Placebo Arm	Total Subjects	Projected Dose
	(n)	(n)		Level

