10.5. Sample Size and Accrual

The proposed total sample size for the study is up to approximately 172 fully evaluable participants. If participants in a dose group drop out or otherwise have missing or unevaluable primary or key secondary virology endpoint data, additional participants may be enrolled to ensure adequate data at each dose level. The total number of participants to be enrolled will not exceed 204.

For Part 1 of the study, the planned sample size is approximately 44 participants who take the first (confirmed) dose of study treatment (approximately 22 each in Arms A and B).

In subsequent, optional study parts, the sample size **for each part** will include approximately 16 participants who take the first (confirmed) dose of study treatment (approximately 12 participants randomized to an active EIDD-2801 arm and 4 randomized to placebo). Participants who are randomized but do not take the first (confirmed) dose of study treatment will not be followed and will be replaced.

This study is designed to evaluate the antiviral activity of EIDD-2801 by estimating the time (days) until elimination of viral RNA detection in NP swabs in people who receive EIDD-2801 compared to those who receive a blinded placebo. Kaplan-Meier estimation will be used with a corresponding exact, stratified log-rank test (for Part 1) and median time (days) until first non-detectable SARS-Cov-2 NP swabs will be estimated in each trial arm.

Power/Sample Size for Part 1:

The distribution of days until SARS-CoV-2 viral RNA is not detectable (i.e., below the limit of quantification in NP swabs) can be compared between the 2 trial arms (drug vs placebo) using an exact log-rank test. At a 0.10 type I error probability and under the assumptions in Figure 8 and the corresponding table below, there is >85% power to detect a difference (Drug - Placebo) of at least 30% if the evaluable sample size is 19 individuals per arm.

Anticipating up to 10% missing data, enrolling n=44 participants total (approximately 22 per arm) in Part 1 will provide 88% power for the primary endpoint. Power was calculated empirically in R version 3.6.2 using 5000 simulated datasets.

- The power to detect a risk difference (RD) (Drug Placebo) of -30% is 0.88.
- The power to detect a RD (Drug Placebo) of -40% is 0.98.
- The power to detect a RD (Drug Placebo) of -50% is >0.99

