10.7.3. Part 1 Analyses

Part 1 will be analyzed separately as an a priori powered study. A Statistical Analysis Plan will be developed that describes the analyses to address the study's primary, secondary, and exploratory objectives.

The following provides an outline of the methods for the main comparisons between randomized arms, particularly for the primary outcome measure.

Analyses involving randomized comparisons will include all randomized participants who received the first (confirmed) dose of study treatment, according to a modified intention-to-treat (m-ITT) approach. Participants who do not receive the first (confirmed) dose will be replaced. Unless stated otherwise, the date of randomization will be the time origin for analysis (Day 1). Additional per-protocol analyses may be performed, particularly for virology efficacy endpoints. Missing data are expected to be uncommon (<5 to 10% of participants). Losses to follow-up will be assumed non-informative and complete-case analyses will be conducted.

This is a virology proof-of-principle study, as such a type I error probability of 10% (α =0.10) will be used throughout, with no planned adjustments for multiplicity or primary or secondary endpoints. Throughout, all statistical tests will be two-sided and "exact" statistical procedures that do not rely on large sample assumptions will be applied where computationally feasible.

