10.9. Interim Analysis

No formal interim analysis is planned.

An interim virology data monitoring report may be prepared after approximately the tenth participant in selected study parts (Parts 1 to 9) have data available through study Day 7. Blinded data listings and pooled descriptive interim summaries of viral RNA and infectious virus may be reviewed to verify assumptions made for sizing this proof-of-concept study, to determine whether

to enroll subsequent dose parts and determine doses to be evaluated in subsequent parts. In addition, the sponsor may choose to review pooled, blinded virology data summaries periodically during enrollment.

A sponsor-designated Data Review Group comprised of a limited number of sponsor personnel may also review unblinded virology data from ongoing cohorts if a sufficient number of subjects have been enrolled. Site personnel will remain blinded until the database is locked at the end of the study. These data may be shared with the IND sponsor.

After completion of each study part, unblinded virology data and safety data may be reviewed to determine the dose(s) for the subsequent parts.

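### Part 1, the only formally tested part, may close anywhere from 24 to about 44 participants, and nothing keeps that decision blind to its unblinded primary-endpoint data

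*Protocol*

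**What the plan says.** **Size of Part 1.** The protocol synopsis (Regimen) states: "Enrollment for Arms A and B may be considered full when at least 24 and up to approximately 44 participants are enrolled". It adds: "Enrollment in Part 1 may be interrupted to initiate enrollment in a different study Part, and may resume at a later time point". Protocol Section 3 repeats the permission to pause and resume, and gives about 44 as an upper limit. Protocol 10.5 treats about 44 as the plan: "the planned sample size is approximately 44 participants who take the first (confirmed) dose of study treatment". SAP Sections 3 and 3.2.1 also plan about 44. The minimum of 24 appears only in the synopsis. No section gives a criterion for declaring Part 1 full or says who decides.

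**Test.** Protocol 10.7.3 states: "Part 1 will be analyzed separately as an a priori powered study". It sets the type I error at 10% without multiplicity adjustment, and adds: "Throughout, all statistical tests will be two-sided". The primary efficacy endpoint is time to undetectable viral RNA, compared by an exact log-rank test; SAP Section 11 drops the stratification. SAP 2.3 says that Parts 2-9 carry no formal hypothesis test.

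**Access to data.** Protocol 10.9 and SAP 4.1 plan no formal interim analysis. They describe a blinded, pooled review to check the sizing assumptions. They then say that a sponsor Data Review Group "may also review unblinded virology data from ongoing cohorts if a sufficient number of subjects have been enrolled". Part 1 is not exempted, and only site personnel are stated to remain blinded.

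**Power.** Protocol 10.5 gives 88% for 44 enrolled (19 evaluable per arm) at a risk difference (RD) of -30%. SAP 3.2.1 gives 88% for 44 enrolled at RD -35%.

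**The concern.** A fixed-size test at 0.10 has its stated error rate only if the decision to stop enrolling does not depend on the comparison being tested. Here the final size is open over a wide range, the comparison may be seen while it is open, and there is no alpha spending, firewall or fixed final number.

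The route is a practical one. Part 1 may be interrupted to start another part, and the synopsis says that later doses are chosen partly on emerging virology from this study. At a first such pause, that virology is Part 1's own. Someone who has seen the Part 1 comparison could then take part in deciding whether Part 1 resumes or is called full.

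Separately, the power figure covers only the top of the permitted range. A reader who takes Part 1 as powered at 88% would be misled if it closed near 24.

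**Working it through.** **Inputs.** The detection probabilities come from the table with Figure 8 (Protocol 10.5).
- Nine-day grid (Days 1, 2, 3, 4, 5, 7, 10, 14, 28): placebo 100, 95, 88, 80, 71, 52, 25, 10, 0%; drug at RD -30% 100, 65, 58, 50, 41, 22, 0, 0, 0%.
- Actual post-baseline swab days (3, 5, 7, 14, 28): placebo 88, 71, 52, 10, 0%; drug is placebo minus the RD, floored at 0.

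The probability of clearance in an interval is S(previous day) - S(this day). For placebo on the swab days this gives 0.12, 0.17, 0.19, 0.42, 0.10. For RD -30% it gives 0.42, 0.17, 0.19, 0.22, 0.

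**Evaluable numbers.** Protocol 10.5 uses 19 per arm after up to 10% missing (22 × 0.9 = 19.8). At 24 enrolled, 12 × 0.9 = 10.8, so 10 or 11 per arm, or 12 if nobody is missing.

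**Power.** Two-sided permutation log-rank test at 0.10, unstratified, no censoring, 6,000 simulated trials, 999 permutations:

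| Setting | 19 per arm | 12 | 11 | 10 |
|---|---|---|---|---|
| RD -30%, nine-day grid | 0.881 | 0.719 | 0.676 | 0.641 |
| RD -35%, actual swab days | 0.880 | 0.706 | 0.671 | 0.635 |
| RD -30%, actual swab days | 0.792 | 0.586 | 0.549 | 0.521 |

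The first row reproduces the protocol's 0.88. The same grid at 19 per arm gives 0.977 at RD -40% (stated 0.98) and 0.999 at RD -50% (stated above 0.99). The second row reproduces the SAP's 88%. On these two rows, closing at 24 leaves about 0.64 to 0.72, a loss of 0.88 - 0.72 = 0.16 to 0.88 - 0.64 = 0.24. The third row must be compared with its own 0.79, a loss of 0.79 - 0.59 = 0.20 to 0.79 - 0.52 = 0.27.

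**Type I error.** Both arms follow the placebo curve on the swab days. Part 1 closes at the first look with exact p ≤ 0.10 in either direction, and otherwise runs to 44 (10,000 trials, 499 permutations per look):

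| Looks (participants) | Probability of rejection |
|---|---|
| 24 only | 0.085 |
| 44 only | 0.097 |
| 24, 44 | 0.145 |
| 24, 34, 44 | 0.168 |
| 24 to 44, every 4 | 0.200 |
| 24 to 44, every 2 | 0.218 |

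The first two rows show that the test holds its level at either size when the size is not chosen on the results. The large-sample log-rank test gives 0.161 to 0.231 for the four multi-look schedules. Counting only rejections in one direction, such as in favour of the drug, it gives 0.083 to 0.117 against a nominal 0.10 / 2 = 0.05.

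The documents give no schedule for unblinded looks, so these schedules are assumptions. The simulation also assumes complete outcomes at each look and no enrolment overrun.

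**The case against.** The case against has four parts.

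**Use of unblinded data.** A reader might infer that the type I error is inflated, or that the sponsor will close Part 1 on unblinded results. The documents support neither. The sizing review is blinded and pooled. Unblinded review after a part is completed serves dose choice. The SAP's one scheduled unblinded analysis follows completion of Parts 1-6, on a cleaned and locked database. No section says who closes Part 1. This stands, and it makes the type I point conditional. It does not remove the point, because the separate permission for ongoing cohorts sets no limit on how the unblinded data are used.

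**Power wording.** Both documents tie 88% to 44 enrolled and neither claims it for 24. This also stands: the figure is not misstated, but a figure for the permitted minimum is missing. It is also tempting to set 0.52-0.59 beside 0.88. That is not like for like, because the same setting gives only about 0.79 at 19 per arm.

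**Consistency.** Protocol Section 3 gives an upper limit, which is compatible with 24 to 44. The mismatch is only between the synopsis and the planned number in Protocol 10.5 and the SAP.

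**Phase.** This is a Phase IIa proof-of-principle study with a deliberately liberal 0.10. That explains the level chosen; it is no reason to leave that level unprotected.

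**Conclusion.** The point holds as a gap in protection. The plan allows the size of its only formally tested comparison to depend on unblinded primary-endpoint data, and has no control against this.

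If closure followed the first significant unadjusted look, exact-test type I error would be about 0.145 with looks at 24 and 44, and up to about 0.22 with a look every 2 participants. For those assumed schedules these are upper bounds: any looser link between looks and closure, or closing only on results that favour the drug, gives less. If closure ignores unblinded data, error stays at or below 0.10.

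The power point does not depend on who sees what. At 24 enrolled, power is about 0.64 to 0.72 on the settings behind the stated 88%, and about 0.52 to 0.59 for RD -30% on the actual swab days. Both ranges rest on the Figure 8 curves and on 10 to 12 evaluable participants per arm.

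**What to change.** 1. In Protocol 10.9 and SAP 4.1, state one of two things. Either the decision to close, pause or resume Part 1 is made only by people without access to unblinded Part 1 virology, or those data are not reviewed until Part 1 enrolment is closed.
2. Reconcile the 24-44 range in the synopsis with the approximately 44 planned in Protocol 10.5 and the SAP, and state the power at the permitted minimum beside the 88%. The minimum of 24 need not be deleted if the closing decision is kept blind.

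The cost is mostly wording. The first option in item 1 needs a separation of roles within the sponsor. The second delays access to unblinded Part 1 data for choosing later parts, which matters most at a first pause, when no later-part data exist. Blinded pooled summaries of Part 1 stay available under either option.

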1. HYPOTHESIS AND STUDY OBJECTIVES

1.1. Hypotheses

- 1.1.1. EIDD-2801 treatment will decrease the time to clearance of SARS-CoV-2 virus in NP specimens from symptomatic SARS-CoV-2 infected adults compared to placebo.
- 1.1.2. EIDD-2801 will be safe and well tolerated in persons with symptomatic SARS-CoV-2 infection.

1.2. Primary Objectives

- 1.2.1. Primary Efficacy Objective To determine if EIDD-2801 reduces the time to viral RNA negativity. Viral RNA negativity will be determined by reverse-transcriptase polymerase chain reaction (RT-PCR) of NP \swabs.
- 1.2.2. Primary Safety Objective To determine the safety and tolerability of EIDD-2801 including 1) any adverse events (AEs) leading to early discontinuation of treatment, 2) study drug-related discontinuation of treatment, 3) new grade 3 or higher AEs (not already present at baseline), and 4) study drug-related new grade 3 or higher AEs.

1.3. Secondary Objectives

- 1.3.1. To determine if EIDD-2801 reduces the time (days) to negativity of infectious virus isolation in NP swabs from SARS-CoV-2-infected adults. Infectious virus isolation is determined by isolation in Vero cell line culture.
- 1.3.2. To compare the incidence of grade 2 or higher AEs and drug-related AEs between treatment arms.
- 1.3.3. To determine if EIDD-2801 reduces the shedding of SARS-CoV-2 RNA in NP swabs compared to placebo as measured by median change in RNA at Treatment Days 3, 5, 7, 14, and 28 as determined by quantitative RT-PCR.
- 1.3.4. To determine if EIDD-2801 increases viral RNA mutation rate. RNA mutation rate is measured by Next Generation sequencing.
- 1.3.5. To determine if EIDD-2801 changes the severity and duration of self-reported symptoms of COVID-19.
- 1.3.6. To determine if EIDD-2801 treatment reduces the proportion of participants who are hospitalized for COVID-19 related illness by Day 28.
- 1.3.7. To characterize the PK of EIDD-2801/EIDD-1931 in patients with COVID-19 following administration of study regimen.

1.3.8. To determine the relationship between drug exposure and viral elimination dynamics including time to clearance.

1.4. Exploratory Objectives

- 1.4.1. To determine if EIDD-2801 will prevent the composite endpoint of hospitalization, oxygen desaturation, oxygen requirement, mechanical ventilation, or death by 28 days after study entry. Hospitalization is defined as ≥24 hours of acute care. Oxygen desaturation will be measured using pulse oximetry. Oxygen requirement will be measured using the World Health Organization (WHO) ordinal scale (see Appendix 1)
- 1.4.2. To determine the comparability between site-collected NP and available OP swabs and available self-collected nasal mid-turbinate swabs for the quantification of SARS-CoV-2 RNA or quantitative culture
- 1.4.3. To determine comparability between viral RNA detection and virus isolation from site-collected NP swabs.

[figure not shown]
2. INTRODUCTION

2.1. Background

2.1.1. Public Health Emergency of International Concern

On December 31, 2019, China reported a cluster of cases of severe pneumonia of unknown etiology in the city of Wuhan to the WHO. The China Centers for Disease Control and Prevention (China CDC) rapidly identified a novel betacoronavirus, SARS-CoV-2, as the etiologic agent with approximately 70% genetic homology with Severe Acute Respiratory Syndrome Coronavirus (SARS-CoV) and 50% homology with Middle Eastern Respiratory Syndrome Coronavirus (MERS-CoV). In the ensuing 4 months, this virus has infected more than 5 million individuals globally with over 345,000 deaths as of the date of this protocol, leading the WHO to declare the COVID-19 outbreak a Public Health Emergency of International Concern⁶.

In the absence of currently approved therapies for SARS-CoV-2 infection and given the rapid spread of this virus with a marked increase in mortality, the identification of an effective therapeutic represents an urgent public health need. As a result, global efforts to identify therapeutic interventions with antiviral or immunomodulatory activity have intensified.

[figure not shown]
After an incubation period of between 2 and 14 days from exposure, approximately 81% of patients develop uncomplicated illness characterized by variable appearance of non-specific symptoms including fever, non-productive cough, dyspnea and myalgias ^{1,7-12}. Approximately, 14% of symptomatic patients develop severe illness often defined by a respiratory rate >30 breaths per minute, oxygen saturation \leq 93%, a partial pressure of arterial oxygen:percentage of inspired oxygen

(PaO2:FiO2) ratio <300, or greater than 50% lung involvement on chest imaging ⁷. An additional 5% of patients become critically ill with respiratory failure, shock and multi-organ dysfunction ⁷. Although asymptomatic infection has been described, the relative proportion of patients who never develop symptoms is not known^{13,14}.

Risk factors for severe disease include older age, male sex, and metabolic syndrome comorbidities including hypertension, diabetes mellitus, and obesity. Markers of a systemic inflammatory response have been reported in association with disease progression and death including D-Dimer, lactate dehydrogenase (LDH) and C-reactive protein (CRP) ^{2,8-11,15,16}. Additionally, cytokine levels including interleukin (IL)1 β , IL1RA, IL7, IL8, IL9, granulocyte-colony stimulating factor (GCSF), granulocyte-macrophage colony-stimulating factor (GMCSF), interferon gamma (IFN γ), inducible protein-10 (IP-10), monocyte chemoattractant protein-1 (MCP1), macrophage inflammatory protein 1 alpha (MIP1 α), macrophage inflammatory protein 1 beta (MIP1 β), tumor necrosis factor alpha (TNF α), platelet-derived growth factor (PDGF) and vascular endothelial growth factor (VEGF) levels were increased among patients admitted to the intensive care unit (ICU) compared with non-ICU patients and healthy adults ⁹. Though low overall relative to acute respiratory distress syndrome (ARDS) and bacterial sepsis, IL-6 is also increased among non-survivors of COVID-19 ¹⁵.

Despite limited data on viral replication dynamics, there is evidence of virus replication in both the upper and lower respiratory tract. Most studies suggest that viral loads are highest in the first week of illness (Figure 1) with long-term viral RNA persistence potentially associated with severity of illness (Figure 2) ^{1,3,5,16,17}. The median time to viral RNA clearance is approximately 11 days for mild disease and 21 days in patients with severe or critical illness (Figure 2) ^{2,17}. Increased viral loads in addition to prolonged virus replication in patients with severe illness suggest that viral loads maybe a useful surrogate for assessing severity in COVID-19.

Viral RNA detection is also dependent upon sample type, with evidence of prolonged viral RNA detection in lower respiratory tract samples including saliva and sputum compared with nasopharyngeal swab samples (Figure 1 and Figure 3) ^{1-3,5,16,17}. Daily sampling of the upper and lower respiratory tract reveal that, in general, viral RNA in OP swabs are elevated in initial samples and already on the decline at the time of presentation whereas sputum samples peak during the first week of symptoms and decline more slowly ⁵.

[figure not shown]
Datapoints denote the mean; error bars indicate SD; slope represents best fit line. The number of patients who provided a sample on each day is shown in the table below the plot. D=days after symptom onset. S=saliva. E=endotracheal aspirate

Less is known about shedding of infectious virus. While infectious virus was readily isolated from clinical samples in a single study, it was again dependent on sample type, viral load, and timing. In the only study to date to evaluate infectious virus kinetics, infectious virus was successfully isolated from 17% of OP swabs and from 83% of sputum samples but only from samples collected within the first week from symptom onset and only in those that contained >10⁶ viral RNA copies/mL (Figure 4). No infectious virus was isolated beyond Day 8 from symptom onset despite elevated viral loads ⁵.

The persistence of infectious virus in the upper respiratory tract has important implications for both transmission and infection prevention and control strategies. SARS-CoV-2 is thought to be transmitted primarily through droplet and contact routes during close unprotected contact between an infected and susceptible individual ¹⁸. Although viral RNA has been detected in air samples within airborne isolation rooms, airborne transmission is not believed to be a major driver of transmission based on current evidence ¹⁹. Recent reports indicate that human-to-human transmission in China is largely driven by familial transmission with secondary attack rates of 3-11%^{14,18,20}. Among 344 clusters including 1308 of 1836 reported cases in Guangdong, approximately 78-85% occurred within families ¹⁸. Identification of interventions to interrupt household and community transmission could have a profound impact on the pandemic at large as well as slow the surge of patients requiring hospitalization and critical care.

